We will explore a number of secondary outcomes. For hospitalisation, we will use all cases of hospitalisation and cases where the main reason for hospitalisation was diabetes, within 2 years of the index date (referral to the scheme). For primary care visits, we will use all visits to primary care within 2 years of the index date. For biological parameters (HbA1c and BMI) we will use the last available measurement within 1 year and 2 years of the index date (since HbA1c and BMI are expected to respond within a shorter period). We have developed relevant methodologies for BMI prediction and have used other methodological tools for multiple imputation of missing data, which we will consider using in this context.

All analyses will be repeated for the secondary outcomes with small changes in the analytic models: Poisson regressions for hospitalisations and primary care visits; linear regressions for HbA1c levels and weight/BMI; Cox proportional hazards regression for deaths. Sensitivity analyses will be used to assess the robustness of the results to different assumptions about patient eligibility, choice of covariates, and modelling options (e.g. multivariable regression instead of matching).

WP 5.2 design 2: For this analysis, we will only use data from the post-intervention period and compare non-diabetic hyperglycaemia-to-diabetes conversion rates. Our main analyses will involve within practice matching, of patients referred to the scheme versus matched patients not referred. However, we will also use across practice matching to control for potential unmeasured confounding in referrals, by matching referring practices to non-referring practices over a set time period, before matching referred patients (from the referring practice) to non-referred patients (from the matched non-referring practice). In the within practice matching we will match patients on age, sex, time of NDH diagnosis and practice. We will attempt to include more controls to increase power (5 to 1, if

possible). In the across practice matching we will match referring to non-referring practices within each English region, and patients will be matched on age, sex and time of NDH diagnosis.

Analyses will closely resemble those in the first design for both the primary (conversion to diabetes) and secondary outcomes (hospitalisation, primary care visits, HbA1c and BMI/weight levels, and death), and we will also investigate effect heterogeneity across regions in this design as well. The power considerations for an intention to treat analysis (comparing not invited and invited) are the same as in the first design. The analyses are potentially subject to confounding due to selection bias (at the patient and practice level, respectively), but no more than other types of comparisons based on CPRD or routinely collected health records. There are a variety of methods available for assessing/adjusting for unmeasured confounding, 105-108 and we will apply selected methods to determine the likelihood that any results could be accounted for by this.

Research question WP 5.3 - What is the long-term impact of the NHS DPP on diabetes prevalence?

If successful, the scheme is designed to lead to a long-term reduction in the population-level prevalence of type 2 diabetes. Therefore we will also undertake a population-level investigation using national datasets of aggregate data. We calculate the power to detect a population-level effect for the NHS DPP. However, these analyses are secondary, since they rest on numerous assumptions.

As noted in WP 5.1, we will describe the national prevalence of diabetes over time, with routinely collected data from general practices used for calculating QOF payments. We have summarised currently available information, for both type 1 and type 2 diabetes. Although the data are aggregated across both types, 90% of diabetes cases are type 2¹⁰⁹ (around 95%). 110-112

The investigation of non-diabetic hyperglycaemia at the population level will require that non-diabetic hyperglycaemia practice registers will become available after the full implementation of the NHS DPP (e.g. like QOF condition registers). Assuming this is the case, we will combine this dataset with ONS data on rurality, deprivation and other covariates we will identify as relevant and measured in the 2011 census. Using methodology which we have developed to link practice level data to low-level population statistics, 113 we will explore the associations between the population characteristics at the Lower Super Output Area level (LSOA: low-level geographies containing an average of 1,500 people). We will also estimate the age-sex adjusted prevalence rates in each LSOA and using both adjusted and unadjusted rates, we will investigate for regional clusters of high prevalence of non-diabetic hyperglycaemia and rapid prevalence increase over time, compared to the national average. This analysis will identify hotspots of non-diabetic hyperglycaemia and will further inform on where best to target capacity for maximum impact. We will use the same approach to map diabetes prevalence, for which data are readily available. In the absence of non-diabetic hyperglycaemia register data we will use the strength of the association between non-diabetic hyperglycaemia and diabetes at the practice level (see WP2) to decide whether the diabetes register can act as a reasonable proxy in identifying hotspots of non-diabetic hyperglycaemia with this methodology.

To statistically assess the short- and long-term effects of the intervention on diabetes prevalence we will use an interrupted time series analysis. ¹¹⁴ The method compares the level and trend in an outcome (e.g. diabetes prevalence) post-intervention, with a prediction made from the pre-intervention level and trend, to look for a significant change. Typically, the pre-intervention trend is assumed to be linear, but this can be tested and curvilinear pre-intervention trends also modelled. For each of the approximately 8,000 GP practices contributing QOF data, we will use interrupted time series to predict diabetes prevalence (i.e. the practice's QOF diabetes register) in each year subsequent to the start of the NHS DPP and compare these predictions to the actual prevalence rates in those years.

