Methods: The primary analysis for assessing the effectiveness of the NHS DPP will use the NDA+MDS if assessed as fit for that purpose, otherwise the work will be done in the CPRD. For robustness, we will address the question using two different research designs.

WP 5.2 design 1: We will use all practices participating in the NHS DPP, and compare the conversion rate from non-diabetic hyperglycaemia to diabetes in patients prior to the start of the NHS DPP to the rate afterwards in equivalent patients. To accomplish this, we will match pre-intervention cases of non-diabetic hyperglycaemia ⁹⁷ to post-intervention cases at the same practice and with the same practitioner if possible (excluding cases with a previous diabetes diagnoses). We will then compare the rates of conversion to diabetes within 2 years between these groups.

Earlier, we confirmed that risk-of-diabetes Read codes are already routinely being used. As the NHS DPP-specific Read codes are not available for patients prior to the scheme, we will conduct an initial exercise to identify the group of pre-existing codes that best identify patients classed as eligible using the NHS DPP-specific codes. We will then use the identified codes to classify patients as scheme-eligible both pre- and post-NHS DPP, to ensure comparability. We will use propensity score methods for the matching. In the logistic regression model to calculate the score we will include: age, sex, region, deprivation, QOF comorbidities and all available biological parameters (e.g. body mass index and HbA1c levels at baseline). Data will be complete for all covariates except the biological parameters, for which we expect a very high level of completeness for this group of patients.

Nevertheless, we will use appropriate multiple imputation methods for longitudinal data if needed. 103

We will compare the conversion rates to diabetes between the two matched groups. Since practices are unlikely to refer all their cases of non-diabetic hyperglycaemia to the scheme (because of capacity limits), we will also compare those patients who were referred to their matched pre-intervention controls, while recognising that this comparison will be subject to confounding with any selection bias.

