The purpose of the scoping study is to identify factors that may influence access to NHS DPP, to help us design a questionnaire for the validation study. Method: we will use data from the qualitative interviews with patients and health professionals in the Access work package to identify important potential influences on access. We will use this to draw up suitable questions, in discussion with patients and clinicians on the Research Advisory Group. We anticipate that this is likely to include factors such as health status, comorbidities, motivation to improve health, health literacy and competing demands (e.g. employment, caring responsibilities).

Step 2: Questionnaire survey

We will undertake a short questionnaire survey of 400 patients (using post, telephone and online methods), to collect data on key patient factors (identified from the scoping study) that are likely to influence the offer and take-up of referral to the NHS DPP (i.e. whether 'NHS DPP referred' patients are referred to and attend the programme), but that are unavailable in routine datasets.

The purpose of the survey is:

- (a) To delineate the role psychological and social factors play in access inequalities, and identify factors potentially addressable by targeted interventions or programme modifications;
- (b) To determine the relative influence of and overall influence of these factors on participation;
- (c) To combine the results with analyses of CPRD, the minimum dataset, and other data sources to assess the extent to which associations between referral, programme attendance, and development of diabetes are confounded with patient characteristics and to adjust the associations for those factors.

The sample will consist of up to 30 patients from each of 20 practices. A suitable approach to sample size estimation for building regression models is to include 20 cases per parameter to be estimated. Our questionnaire includes 20 predictors (some of the questions will be combined into composites), giving us a recruitment target sample size of 400. To achieve this we are approaching a total of 600 patients.

Practices will produce a list of people at risk of diabetes who have been referred to DPP at least 3 months ago. After checking the list, practices will use a randomisation list provided by researchers to randomly select patients in a 1:1 ratio according to whether they are:

- (a) 'NHS DPP non-attenders', referred to NHS DPP but who did not attend any sessions

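### WP 5.2 design 2 does not commit its main referred versus non-referred contrast to design 1's baseline covariates, across-practice matching only lessens patient-level selection, and WP6 cannot adjust referral associations

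*Protocol*

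**What the plan says.** **Design 1 (Protocol, WP 5.2 design 1).** Pre- and post-programme cases are matched by a propensity score. Besides age, sex and region, the score includes "deprivation, QOF comorbidities and all available biological parameters (e.g. body mass index and HbA1c levels at baseline". The outcome models that follow name only a region covariate.

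**Design 2, main contrast (WP 5.2 design 2).** "Our main analyses will involve within practice matching, of patients referred to the scheme versus matched patients not referred". The matching set is then given: "In the within practice matching we will match patients on age, sex, time of NDH diagnosis and practice".

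**Design 2, across practices.** "However, we will also use across practice matching to control for potential unmeasured confounding in referrals". Referring practices are first matched to non-referring ones within region, "before matching referred patients (from the referring practice) to non-referred patients (from the matched non-referring practice"; here "patients will be matched on age, sex and time of NDH diagnosis".

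**Design 2, limitations.** The analyses are said to resemble those of design 1 closely. They are also acknowledged to be "potentially subject to confounding due to selection bias (at the patient and practice level, respectively", and selected methods for unmeasured confounding are promised.

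**WP6 (Step 2, Questionnaire survey).** "Practices will produce a list of people at risk of diabetes who have been referred to DPP at least 3 months ago". The two groups drawn from that list are attenders and referred patients who attended no session. Purpose (c) and the Analysis paragraph nevertheless claim assessment and adjustment of associations between referral, as well as attendance, and later diabetes.

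**The concern.** The Protocol itself says (WP 1.2) that both GP and patient may influence referral, so referred and non-referred patients are likely to differ at baseline. HbA1c and BMI bear directly on conversion to diabetes and plausibly on referral. Design 2 is more exposed to this selection than design 1's all-eligible comparison, yet it names the thinner covariate set. Adding across-practice matching could suggest that patient-level selection has been dealt with, and the word respectively in the limitations sentence encourages that reading. If both versions of design 2 lean the same way, their agreement reassures less than it seems to. WP7 uses a comparison of conversion with and without the programme as a model input, so a bias could carry into cost-effectiveness.

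**Working it through.** **1. The plan's own figure.** Design 2 takes its power from design 1: 7.5% versus 5.625% at 2 years, alpha 5%, 90% power, 1:1.

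- Mean proportion 0.065625, difference 0.01875.
- n per arm = [1.960·√(2 × 0.065625 × 0.934375) + 1.2816·√(0.075 × 0.925 + 0.05625 × 0.94375)]² / 0.01875² = 3,664, or 7,328 in total. The Protocol gives 7,331, so it reproduces with a two-sided test.
- Risk ratio 0.05625/0.075 = 0.75. This is the scale on which to judge a bias.

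**2. Where the covariates enter.** Design 1 brings HbA1c, BMI, deprivation and comorbidities in through its propensity score, not its outcome models. Design 2 replaces that matching with its own shorter list. Resembling design 1's analyses therefore does not by itself carry these covariates across. The sensitivity analyses on choice of covariates, described under design 1, are not the main contrast.

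**3. What across-practice matching does to selection.** Let q be the share of high-risk patients among all eligible patients, q_R the share among the referred, q_N the share among the non-referred, and f the fraction referred. Assume referring and non-referring practices have the same case mix.

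- q = f·q_R + (1 − f)·q_N, so q − q_R = (1 − f)(q_N − q_R).
- Within practice the controls have share q_N; across practices they have share q. The imbalance left is (1 − f) of the within-practice one: 90% at f = 10%, 70% at 30%, 50% at 50%.

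**4. Illustrative size, with no programme effect.** All inputs in this step are assumptions. With k the risk ratio between strata, the spurious risk ratio is [1 + (k − 1)q_R] / [1 + (k − 1)q_control].

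- Example: q = 0.30, k = 3, odds of referral halved in the high-risk stratum, f = 0.30. This gives q_R = 0.205 and q_N = 0.341.
- Within practice: 1.410/1.682 = 0.84. Across practices: 1.410/1.600 = 0.88.
- Share left: (0.300 − 0.205)/(0.341 − 0.205) = 0.70, as in step 3.

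Over q = 0.3 or 0.5, k = 2 to 4 and f = 10% to 50%:

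| Odds of referral in high-risk stratum | Within practice | Across practices |
|---|---|---|
| Halved | 0.797–0.903 | 0.818–0.945 |
| Doubled | 1.114–1.257 | 1.055–1.225 |

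At 3,666 patients per arm and 7.5% control risk, a spurious ratio of 0.84 would be declared significant about 53% of the time.

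**5. The same structure elsewhere in the Protocol.** Design 1's second comparison sets referred patients against matched pre-intervention controls. That is also a selected group against an unselected pool, and the Protocol says it is subject to confounding with selection bias. Across-practice matching has the same structure, so the same caution applies.

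**6. WP6.** Everyone in the frame has been referred, so referral does not vary. The probability of referral given patient characteristics cannot be estimated from this sample. The probability of attendance among the referred can.

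**The case against.** Much of the opposing case stands, and it rules out several stronger readings.

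- **That design 2 leaves HbA1c and BMI out altogether.** The text lists matching variables, not outcome-model covariates. Matching on a few variables and adjusting for the rest by regression is ordinary practice, and the SAP, which is not shown, may name them. What stands is that the Protocol makes no such commitment for the main contrast.
- **That across-practice matching achieves nothing.** It removes a share f of the patient-level imbalance, half of it at f = 50%. The two versions of design 2 therefore do not carry identical bias.
- **That the Protocol hides selection bias or offers no other remedy.** It admits the bias and promises further methods for unmeasured confounding. These are unnamed, and are to judge how likely it is that confounding explains a result.
- **That WP 5.2 as a whole lacks a check.** Design 1's comparison of all eligible patients before and after the programme is not exposed to selection into referral.
- **That design 2 relies on WP6.** Design 2 does not cite it, and WP6 says that WP5 and WP7 do not depend on the survey. The WP6 point is a separate, narrow mismatch between its frame and its claim.
- **That the bias is known to be large.** Nothing in the documents anchors its size or direction. The eligible HbA1c band is only 42–47 mmol/mol, which limits how far mean HbA1c can differ between groups.

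**Conclusion.** The concern holds in three limited parts. First, the Protocol does not commit design 2's main contrast to baseline HbA1c, BMI, deprivation and QOF comorbidities, although design 1 uses them. Second, the across-practice version lessens patient-level selection to a share (1 − f) and adds possible practice-level differences, so the limitations sentence should not be read as leaving practice-level bias only. The share (1 − f) is exact if the two sets of practices have the same case mix. Third, WP6 cannot support adjustment of referral associations.

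The spurious ratios of about 0.80 to 1.26 (within practice) and 0.82 to 1.23 (across practices) rest wholly on assumed selection strength. They show that moderate selection would matter against a target of 0.75; they do not estimate the actual bias. Adjusting for the four covariates deals only with selection that runs through them, so the promised methods for unmeasured confounding are still needed.

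**What to change.** 1. **Covariates.** In WP 5.2 design 2, name baseline HbA1c, BMI, deprivation and QOF comorbidities in the primary outcome model or propensity score, for both the within- and across-practice versions. Cost: wording and code on data design 1 already plans to use. Design 1 expects very high completeness for the biological measures and provides for multiple imputation if needed.
2. **Across-practice contrast.** State that it carries patient-level as well as practice-level selection. Add, as a supporting analysis, an unscaled comparison of all eligible NDH patients in referring practices with all those in matched non-referring practices, with practice-clustered standard errors. Under the equal case-mix assumption this takes out patient-level selection into referral; practice-level confounding remains. The cost is dilution and lost precision. If a ratio of 0.75 applied to referred patients of average risk, the contrast would show 1 − 0.25f, that is 0.975 at f = 10%, 0.925 at 30% and 0.875 at 50%. Scaling by the referral proportion is optional and must state its assumption that a practice's referring status affects conversion only through referral. WP 5.3 gives reason for doubt, since it warns that the programme itself may lead to less severe cases being diagnosed.
3. **WP6.** Limit the adjustment claim in purpose (c) and the Analysis paragraph to attender versus non-attender contrasts among referred patients. Cost: a narrower claim, with no new fieldwork.

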It is also the case that not all practices will be referring to the NHS DPP in the first few years, and the introduction of the scheme will be gradual. Provided that information on participating practices becomes available, we will use it to compare trends between practices that are, and are not, accessing the NHS DPP, under the interrupted time series analysis. This will allow us to use the non-participating practices as a comparator group to better adjust the analyses for potential post-NHS DPP trend changes, not attributed to the NHS DPP, and conduct additional tests on our assumptions.

Post-NHS DPP, once we have completed our analyses, we will be able to revisit this section and scrutinize the assumptions made. We will combine our estimates of the incidence rate of non-diabetic hyperglycaemia and rate of conversion to diabetes, and the impact of the NHS DPP with population-level data, to make forward projections of:

- (i) future rates of diabetes incidence and prevalence, under differing assumptions about the numbers of NHS DPP places on offer
- (ii) what these trends would have been without the NHS DPP, and the reduction attributable to the NHS DPP.

This analysis will help to determine the intervention capacity required to produce a sustainable reversal in the current trend of increasing rates of both non-diabetic hyperglycaemia and diabetes.

The risks of not obtaining sufficient data for these analyses are closely linked to practice participation to the scheme, a parameter that is out of our control. With the CPRD we have 13% of UK primary care cover, which is representative in terms of deprivation and geography. If the uptake of the scheme is very poor, we may not be able to identify enough cases in the databases. Another potential risk would be if the practices contributing data to the databases were less likely to participate in the scheme. This is highly unlikely, however, since these are generally large and well organised practices and we would expect them to be keen to increase their income through participation to the scheme.

Data linkage

Within the dataset we will have access to information on personal characteristics, diagnoses of non-diabetic hyperglycaemia (NDH - and its predecessors impaired glucose regulation – IGR - and impaired glucose tolerance - IGT), exposure to the NHS-DPP and the primary outcome (progression to diabetes).

There will be no need for us to link patient-level variables from different data sources. CRPD data has already been successfully linked to Hospital Episode Statistics (HES) and Office for National Statistics (ONS) data, allowing the construction of a more complete patient journey through primary and secondary care and the mapping of causes of mortality (e.g. diabetes, cardiovascular).

To complement the patient level analyses and deliver a more complete evaluation of the scheme, we will also use various national databases of aggregate data such as NDA at the practice or low geographical level. The aggregate datasets will be linked at the practice level using the NHS practice ID, and then all relevant data will be linked using the NHS attribution dataset (which links primary care patients to ONS lower super output areas using their residence postcode) to low-level geographical areas where they will be combined with deprivation and relevant census covariates. The patient-level data and the aggregate data databases will not be linked.

Work package 6 - Validation Study ([name] and [name])

Aims: To assess the risk of confounding in participation in NHS DPP and allow adjustment in other work packages

Rationale: The comparison in the effectiveness (WP 5) and cost effectiveness (WP 7) work packages are between those who do and do not participate in NHS DPP. However, in this observational comparison the influence of unmeasured confounders (that is, factors that have an effect on both DPP participation and progression to diabetes), cannot be excluded. To better evaluate the risk of confounding and adjust for it, we propose a validation study to collect data on the key potential barriers to access and confounders unavailable from the routine records, to inform the analysis and increase the robustness of our findings.

Methods:

Step 1: Initial scoping study

The purpose of the scoping study is to identify factors that may influence access to NHS DPP, to help us design a questionnaire for the validation study. Method: we will use data from the qualitative interviews with patients and health professionals in the Access work package to identify important potential influences on access. We will use this to draw up suitable questions, in discussion with patients and clinicians on the Research Advisory Group. We anticipate that this is likely to include factors such as health status, comorbidities, motivation to improve health, health literacy and competing demands (e.g. employment, caring responsibilities).

Step 2: Questionnaire survey

We will undertake a short questionnaire survey of 400 patients (using post, telephone and online methods), to collect data on key patient factors (identified from the scoping study) that are likely to influence the offer and take-up of referral to the NHS DPP (i.e. whether 'NHS DPP referred' patients are referred to and attend the programme), but that are unavailable in routine datasets.

The purpose of the survey is:

- (a) To delineate the role psychological and social factors play in access inequalities, and identify factors potentially addressable by targeted interventions or programme modifications;
- (b) To determine the relative influence of and overall influence of these factors on participation;
- (c) To combine the results with analyses of CPRD, the minimum dataset, and other data sources to assess the extent to which associations between referral, programme attendance, and development of diabetes are confounded with patient characteristics and to adjust the associations for those factors.

The sample will consist of up to 30 patients from each of 20 practices. A suitable approach to sample size estimation for building regression models is to include 20 cases per parameter to be estimated. Our questionnaire includes 20 predictors (some of the questions will be combined into composites), giving us a recruitment target sample size of 400. To achieve this we are approaching a total of 600 patients.

Practices will produce a list of people at risk of diabetes who have been referred to DPP at least 3 months ago. After checking the list, practices will use a randomisation list provided by researchers to randomly select patients in a 1:1 ratio according to whether they are:

- (a) 'NHS DPP non-attenders', referred to NHS DPP but who did not attend any sessions
- (b) NHS DPP attenders.

In practices where DPP attendance is not recorded we will send questionnaires to referred patients and ask about NDPP attendance as part of the questionnaire, to place each individual responder in the relevant attenders or non-attenders group. On average, 50% of people referred to DPP attend the programme, so this approach should result in roughly equal groups. Additionally, in practices which hold clinics to review patients at risk of diabetes, study information can be provided to eligible patients.

A high recruitment rate is essential to minimise bias in the validation sample. The questionnaire will be as short as practicable. We will use intensive recruitment and collection methods, working closely with professionals and the NIHR CRN locally, piloting the questionnaire prior to use with patients, and using financial incentives to patients and practitioners, ¹¹⁶¹¹⁷ aiming for a 70%-80% recruitment rate.

The high response rate required means that this work-package is 'high-risk'. If we manage to reach this target then our findings in this section will augment the quality of the analyses in work-package 5 and 7. However, the analyses in those work packages are not dependent on the success or otherwise of this survey. If a lower response rate is evident, the data will still be of considerable value, as it will allow us to examine the role of psychological and social factors in access inequalities, and study the relative influence of GPs and patient self-selection on NDPP participation.

Analysis: Descriptive statistics will be used to characterise the groups of people who attend, and do not attend, the DPP across a range of demographic, attitudinal and psychological factors; and comparisons will be made to available national data (e.g. from the DPP "minimum dataset"). We will use univariate and multivariate logistic regression methods to estimate and compare the role of the various factors in influencing attendance at the NHS DPP intervention. We will also compute a propensity score for each individual representing their probability of attending given their particular combination of factors, to provide a picture of the extent to which these factors as a whole are associated with attendance. The individual factor and propensity scores will further be used in combination with analyses of CPRD, the minimum dataset, and other data sources to assess the extent to which any observed associations between DPP referral and attendance and subsequent development of diabetes are confounded with demographic differences and to adjust the associations for those differences. These results will further feed into the health economics analysis of the cost-effectiveness of the programme, particularly in relationship to estimating effectiveness in patient sub-populations.

Work package 7 - Comparative Long-term Cost Effectiveness ([name] and [name])

Aims: To assess whether the NHS DPP is cost-effective compared to usual care in terms of long-term costs and benefits

Rationale: As with work package 5, commissioning of the NHS DPP will also be dependent on a rigorous demonstration of cost-effectiveness. Diabetes is associated with compromised quality and length of life and significant long-term health care utilisation. Effective prevention has the potential to generate health benefits and significant cost-savings over the longer term. This work package will utilise economic modelling to explore the longer term costs and benefits of the NHS DPP.

Overview of methods: This work package will estimate the overall cost effectiveness of the NHS DPP taking account of the costs incurred by commissioners to deliver the programme and the long-term health benefits for participants and non-participants. It will draw together the findings of the other work packages and use an economic model to summarise the overall cost-effectiveness of the programme as implemented and identify major opportunities for enhancing its cost effectiveness.

Research questions WP 7.1 - What are the additional costs of implementing and providing NHS DPP to the range of commissioning agencies involved?

Methods: We will estimate the additional costs of implementing and providing NHS DPP using information from the national commissioning agencies and the Implementation work package (WP2). These costs will include the contracted amounts paid to the NHS DPP providers and the costs to general practices of identifying, referring and following-up on 'NHS DPP eligible' patients. We will need to identify the additional costs incurred by general practices due to the introduction of the NHS DPP, excluding the costs that they would incur anyway in identifying and managing this patient group. We will also examine whether general practices transfer the costs of providing services to the target group as a result of the introduction of a targeted scheme for these patients paid for by other means.

Research questions WP 7.2 - What are the short-term health benefits of NHS DPP to participants in the scheme, and what are the cost consequences of the short-term changes in health service utilisation for participants in the NHS DPP?

Methods: We will use data from the Outcomes work package (WP4) to estimate the average increases in health-related quality of life reported by NHS DPP participants. We will model the expected effects on quality of life using mapping to the EQ5D 5L. We will use data from participants on health service utilisation and figures from NHS Reference Costs and the Unit Costs of Health and Social Care to estimate the changes in costs. We will focus initially on the short-term effects reported by participants.

Research questions WP 7.3 - What are the expected long-term health benefit consequences of the introduction of NHS DPP? What are the expected long-term cost consequences of the NHS DPP?

Methods: NHS DPP is designed to increase individual awareness and help them to reduce their risks through lifestyle changes. We will use the ELSA (2004-2014) data to: a) estimate the benefits of lifestyle changes on the diagnosis of diabetes; and b) estimate the effect of diagnosis itself on lifestyle changes. We will use multivariable non-linear regression models to predict the benefit of lifestyle changes (measured by physical activity, BMI, consumption of fruit and vegetables) on the likelihood of developing diabetes for those who are at risk of diabetes in the first observation in ELSA (using glucose level measurements in ELSA). We will estimate these benefits by age and gender.

We will then determine the wider behavioural effects of the NHS DPP that arise from a non-diabetic hyperglycaemia diagnosis. International evidence suggests that individuals improve their lifestyles in response to diagnosis. However, patients with non-diabetic hyperglycaemia could also decide to indulge in less healthy lifestyles anticipating increased and effective treatment in the future. We will estimate this behavioural response using dynamic models of lifestyle choices and comparing diabetics to a statistically defined group of people at 'risk' of developing diabetes using the propensity score model 121 using a similar US survey, the Health and Retirement Survey.

Research questions WP 7.4 - Is the overall NHS DPP cost-effective compared to usual care? How does incorporation of equity consequences affect the overall cost effectiveness of NHS DPP? What changes to the NHS DPP would improve its short and long-term cost effectiveness?

Methods: It is expected that the NHS DPP will increase costs in the short term as participants make greater use of health services to better identify and manage their newly-identified needs. Health-related quality of life may also deteriorate in the short term as participants adjust to the discovery that they are at higher risk. As such, it is likely that the health benefits and cost reductions that are expected from the NHS DPP will be accrued in the longer-term.

Decision-analytic models are frequently used within economic evaluations, to extrapolate beyond observed data and to estimate the long-term effects of an intervention. Often, this involves modelling a hypothetical cohort over a lifetime horizon, using multiple sources of data. Inputs into decision-analytic models include parameters such as the probabilities of different events occurring (referred to as transition probabilities), the costs associated with events or resource use, and utility scores, which can be used to estimate quality-adjusted life years (QALYs).

Several decision-analytic models exist in the published literature*, which evaluate the cost-effectiveness of prevention strategies of developing Type 2 Diabetes. These models will be assessed to determine their strengths, weaknesses, validity and usability. In light of these assessments, one of the existing models will be selected and adapted, so that it can be used to evaluate the cost-effectiveness of the NHS DPP. As there is no model that currently evaluates the effectiveness of the NHS DPP, we will require effectiveness data to inform the model parameters.

The National Diabetes Audit (NDA) contains information on all of the patients identified as being at risk of developing Type 2 Diabetes, as well as the number of these that go on to develop the condition. This data will be used as an input in the decision-analytic model, comparing the number developing diabetes who have accessed the NHS DPP to those who receive usual care. Access to the data will conditional on an application to NHS Digital, which will be reviewed by an Independent Group Advising on the Release of Data (IGARD), who determine whether the application is ethically acceptable, and that the appropriate data governance structures are in place.

Other data sources will include, the costs associated with implementing and running the NHS DPP, costs associated with the condition of Type 2 Diabetes, and published clinical data on the risk of various comorbidities and complications which arise as a result of Type 2 Diabetes.

